8.3 Secondary Safety Variable

The secondary safety endpoint will be determined by evaluating the number of Serious Adverse Events (all SAEs included) within 28 days of the enrolment and the rescue therapy requirement (APRV, high frequency ventilation, ECCO2R and ECMO).

Tabulations of the number of subjects who experienced AEs as well as severity of the events will be presented overall and by system organ class and preferred term. SOCs will be ordered by frequency (highest frequency first). PTs will be ordered alphabetically per SOC. Subjects will only be counted once for each preferred term. In case a subject experienced the same event more than once, the worst severity will be presented.

The following non-mechanical ventilation related adverse events recorded on study day 7 and 28 will also be considered as additional secondary safety variables.

• Severe Acute kidney injury (AKI) in need for CRRT/IHD

- Severe critical illness neuro-myopathy signs of tetraplegia affecting arms shoulder and neck with potential implication of respiratory muscle. Weakness is documented using the following score points: score 0 for no visible muscle contraction, score 1 for visible muscle contraction with no or trace movement, score 2 for limb movement, but not against gravity and score 3 for movement against gravity but not resistance.
- Severe critical illness encephalopathy leading to prolongation of mechanical ventilation. The most frequent causes being a metabolic or electrolyte disorder, systemic inflammation and other causes. Hypoxia, Stroke, intracranial bleeding, epilepsy, and delirium. Encephalopathy is assessed using the GCS score and need to be reported is < 8 points.
- Withhold of weaning and/or withdrawal of mechanical ventilation because of treatment limitation related to patient wish or treatment futility due to irreparable single or multi-organ failure affect mechanical ventilation strategy, weaning from mechanical ventilation up to withdrawal of mechanical ventilation.
- Extubation failure that is related to weaning process by itself, or associated conditions based on the interpretation of the investigator.
- Need for tracheostomy that is related to a difficult weaning process or associated conditions based on the interpretation of the investigator.

Secondary safety variables will be performed on the safety population.

8.4 Tertiary Safety Variable

The tertiary safety variable will be calculated as the percentage of time spent with **at least one** of the six variables in the sub-optimal target ranges during ventilation period **from day 8 up to day 28** after randomization:

- 1) Tidal volume (VT)
- 2) Maximum pressure (Pmax)
- 3) Oxygen saturation measured by pulse oximetry (SpO₂)
- 4) End-tidal partial pressure of carbon dioxide (PetCO₂)
- 5) Respiratory rate (RR) for spontaneous breathing subjects
- 6) Pmax-PEEP for passive ARDS subjects

The tertiary safety variable will be expressed by median (interquartile range). Log transformation will be performed on the data before performing the 2 sample Z-test. Comparisons will use the 2 sample Z-test for log transformed variables. The P values <0.025 (one-sided, the hypothesis is that INTELLiVENT-ASV is better than conventional non-automated ventilation in terms of efficacy) will be considered significant.

Tertiary safety variable will be performed on the safety population.

8.5 Adverse Events and Serious Adverse Events

Adverse events (AEs) will be coded using the IMDRF terminologies for categorized Adverse Event Reporting (Version 5.0) and will be graded according to the National Center Institute Common Terminology Criteria for AEs (NCI-CTCAE criteria [v5.0]). Adverse events will be analyzed in terms of their type, incidence, severity, and relationship to the study treatment.

Related AEs are defined as events with a relationship to mechanical ventilation, study procedure and INTELLiVENT-ASV equal to 'Not related', 'Related'.

A summary table will present by treatment arm the number and percentage of subjects with at least one of the adverse events, adverse device effects or observed device deficiencies.

The following tabulations will be presented:

Non-Device-Related:

- Adverse Event (AE)
- Serious Adverse Event (SAE)

Device/Procedure-Related:

- Adverse Device Effect (ADE)
- Serious Adverse Effect (SADE)
- Anticipated SADE (ASADE)
- Unanticipated Serious Adverse Device Effect (USADE)

For detailed categorization of Adverse Events, refer to protocol section 9 safety and ANNEX A in the protocol.

Listings of all adverse events by treatment arms will be provided, flagging the ones that are Device/Procedure-Related.

The relationship between the use of the medical device (including the medical - procedure, i.e., invasive mechanical ventilation) and the occurrence of each adverse event will be assessed and categorized.

Each SAE will be classified according to four different levels of causality.

- 1. Not related to the device in question
- 2. Possible
- 3. Probable
- 4. Causal relationship

A frequency table will be provided to assess the relationship of the serious adverse event to INTELLiVENT-ASV.

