9.1.2 Adverse Events (AEs)

ISO 14155 / MDR 2017/745 Definition (regulatory definition):

An AE is any untoward medical occurrence, unintended disease or injury or any untoward clinical signs, (including an abnormal laboratory finding,) in subjects, users or other persons, in the context of a clinica investigation, whether or not related to the investigational medical device. and whether anticipated or unanticipated.

NOTE 1 to entry: This definition includes events related to the investigational medical device or the comparator.

NOTE 2 to entry: This definition includes events related to the procedures involved.

NOTE 3 to entry: For users or other persons, this definition is restricted to events related to investigational medical devices.

Specificities to EASiVENT:

The following Adverse Events (**AEs**) **will be recorded during** the EASiVENT Study Days 0 through 28:

1. Serious Adverse Events (SAEs) other than those listed as study-specific outcomes
2. Non-serious AEs that are considered by the investigator to be possibly, probably, or definitely (causally) related to mechanical ventilation as a supportive measure for acute respiratory failure.
For details please refer to EASiVENT Study list of Adverse Event, [Annex D](#)
3. AEs that lead to permanent discontinuation of INTELLiVENT-ASV-Management.

Investigators will be instructed to record their assessment of the potential relatedness of each Adverse Event (AE) to protocol procedures and mechanical ventilation. Potential relatedness of an event to mechanical ventilation will be determined by evaluating the temporal relationship and if the event is unanticipated or unexplained given the patient's clinical course, care, and previous medical conditions. The degree of certainty the investigator has regarding relatedness of the event to mechanical ventilation will be recorded as not related, possibly related, probably related, or definitely (causal) related. If patient's INTELLiVENT-ASV-Management is discontinued as a result of an AE, study site personnel will clearly record in the eCRF of the Study the circumstances and data leading to discontinuation of INTELLiVENT-ASV as ventilation mode.

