9.2.1 Device deficiency (ISO 14155)

Inadequacy of an medical device related to its identity, quality, durability, reliability, usability, safety or performanc

9.2.2 Adverse Device Effect (ADE) (ISO 14155)::

Adverse event related to the use of an investigational medical device.

NOTE 1: This includes any adverse event resulting from insufficiencies or inadequacies in the instructions for use, the deployment, the implantation, the installation, the operation, or any malfunction of the investigational medical device.

NOTE 2: This also includes any event that is a result of a use error or intentional abnormal use of the investigational medical device.

Note 3 to entry: this includes 'comparator' if the comparator is a medical device.

9.2.3 Serious Adverse Device Effect (SADE) (ISO 14155):

Adverse device effect that has resulted in any of the consequences characteristic of a serious adverse event.

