Missing AE intensities will not be imputed. Such AEs will be included in summaries by including a category of "missing" in the tables. If the assessment of the relationship of the AE to investigational device is missing, we will assume that the AE is possibly related to investigational device.

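### SAP 8.5 lists 'Not related' among the ratings that make an adverse event related, so the rule cannot separate related from unrelated events

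*SAP*

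**What the plan says.** The rule is in SAP 8.5: "Related AEs are defined as events with a relationship to mechanical ventilation, study procedure and INTELLiVENT-ASV equal to 'Not related', 'Related". It is current text, not an entry in the version history, and no other section corrects it.

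Other places describe relatedness differently:

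- SAP 8.5, a little further on: "Each SAE will be classified according to four different levels of causality". The levels are not related, possible, probable and causal.
- Protocol 9.1.2, on relatedness to mechanical ventilation: the investigator's degree of certainty "will be recorded as not related, possibly related, probably related, or definitely (causal) related".
- SAP 4.8, for a missing device relationship: "we will assume that the AE is possibly related to investigational device".
- Protocol 9.2.2, on an adverse device effect: "Adverse event related to the use of an investigational medical device".

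SAP 8.5 also plans outputs that need a working split. It divides its tabulations into Non-Device-Related and Device/Procedure-Related groups, and it states: "Listings of all adverse events by treatment arms will be provided, flagging the ones that are Device/Procedure-Related".

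**The concern.** A definition of related events has to leave the unrelated ones out. This one names the negative rating as qualifying. It has two further faults. It uses two levels where the protocol and the rest of SAP 8.5 use four, with no mapping between them. It also joins ventilation, procedure and device with 'and', without saying whether one positive rating is enough or all three are needed.

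At stake is the related/unrelated split of AEs in a trial whose synopsis names it as the primary basis for a pre-market approval application. A programmer could not follow the sentence and obtain a meaningful split. The threshold and the any-or-all rule would then be chosen during programming, without a prespecified basis.

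**Working it through.** No sample size, power or event count is involved. The check is to apply the sentence to each possible rating and see what it selects.

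**Inputs.** Three relationships (mechanical ventilation, study procedure, INTELLiVENT-ASV) and two qualifying values ('Not related', 'Related'), from SAP 8.5. Four-level scales, from Protocol 9.1.2 (ventilation) and SAP 8.5 (SAEs). The missing-rating rule, from SAP 4.8.

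**Step 1: the sentence's own two-level scale.** Each relationship takes one of two values, giving 2 × 2 × 2 = 8 patterns. Both values qualify, so all 8 of 8 patterns meet the definition, whether one relationship or all three must qualify. Every rated AE counts as related. The same follows if possible, probable and definite are first collapsed into 'Related', but the SAP does not state that step.

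**Step 2: literal matching to the four-level labels, for any one relationship.**

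| Rating | In the SAP 8.5 definition? | Expected class |
|---|---|---|
| Not related | Yes | Not related |
| Possible | No | Related |
| Probable | No | Related |
| Definite / causal | No | Related |
| Missing device rating, set to possible (SAP 4.8) | No | Related |

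Only one of the four levels is selected, and it is the wrong one.

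**Step 3: treat 'Not related' as a slip and delete it.** On the two-level scale:

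- any one relationship is enough: 8 − 1 = 7 of 8 patterns are related;
- all three are required: 1 of 8 patterns is related.

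The choice matters between arms. INTELLiVENT-ASV is not selected in the control arm (Protocol 3.1), so if all three are required, a control event could not ordinarily qualify. If any one is enough, the non-serious AEs recorded under Protocol 9.1.2 because they are judged related to ventilation qualify automatically.

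**Step 4: are there unrelated AEs to separate?** Yes. Protocol 9.1.2 records SAEs other than study-specific outcomes, and items 5 to 7 of the SAE list in Protocol 9.1.3 (hypercapnic acidemia, hypocapnic alkalemia, hypoxemia) carry no relatedness condition.

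**Step 5: what depends on the split.**

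| Output | Affected? |
|---|---|
| Device/Procedure-Related versus Non-Device-Related tabulations (SAP 8.5) | Yes: needs a working split |
| Flags in the AE listing (SAP 8.5; Listing 16.02.07.02) | Yes: needs a working split |
| Deaths by device/procedure relatedness (SAP 8.6) | Inconsistent with the rule, though SAP 8.6 does not cite it |
| SAEs by causality level (Table 14.03.09) | No: SAP 8.5 gives four causality levels for SAEs |
| Number of SAEs, all included (SAP 8.3) | No: relatedness not used |
| Co-primary endpoints (SAP 7.1, 8.2) | No |

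**The case against.** The best defence is that the sentence is a garbled list of the form's answer options. The same section needs a non-device-related group, so its authors cannot have meant to include unrelated events. SAP 8.5 also refers to Protocol section 9 and Annex A for detailed categorisation. Sections 9.2.2 to 9.2.7 there define the adverse device effect categories without using this sentence, and the medical monitor and DSMB assess relatedness independently.

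Much of this stands. It limits the consequence, and it means one cannot say that the device-effect categories rest wholly on the SAP sentence. It does not repair the sentence. Protocol section 9 contradicts it, and a typographical reading still leaves the mapping and the any-or-all rule open, as Step 3 shows. The categorisation charts (Protocol Figures 1 and 2) are not in the text reviewed; whatever they show, the SAP sentence would still need to be reconciled with them.

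A reader might go further and infer that device-related counts would be greatly inflated, given expected mortality of around 30% (Protocol 9.1) and much illness-driven morbidity. The documents do not support that. Under Protocol 9.1.1, death from the underlying illness and the other listed illness events are study-specific clinical outcomes. They are generally not recorded as AEs unless judged related to ventilation or, deaths excepted, unless they end the study intervention. Protocol 9.1.3 likewise limits SAE deaths to those not due to the underlying illness or possibly, probably or definitely related to study procedures. Most of the events behind the 30% therefore do not enter the AE set.

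**Conclusion.** The sentence is wrong as written and should be corrected. It excludes no rated AE on its own two-level scale (8 of 8 patterns), and it selects only the 'Not related' level if matched literally to the four-level labels. Either way it cannot produce the split that SAP 8.5 itself requires.

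The statement that every AE becomes related is conditional: it needs the two-level reading, or the graded levels collapsed to 'Related'. The size of any miscount cannot be derived from the documents, because they give no AE counts by rating.

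The fault is confined to the related/unrelated tabulations and flags, with an inconsistency in the death classification. A reader might also infer that the trial's main safety conclusion is compromised. It is not: the primary safety endpoint is time in the sub-optimal range, and the secondary SAE count ignores relatedness. Type I error and sample size are not touched.

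One assumption remains. The case report form (version 6.0, cited in SAP section 2) was not available, so the scale collected for each relationship is not known. The protocol states the four-level scale only for mechanical ventilation.

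**What to change.** Replace the sentence in SAP 8.5 with a rule that does the following:

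1. Removes 'Not related' from the definition of related.
2. Counts possible, probable and definite/causal ratings as related (or 'Related' where the form has two levels), and only 'Not related' as not related.
3. Applies this separately to INTELLiVENT-ASV, mechanical ventilation and study procedure, following the scale collected for each, in place of joining them with 'and'.
4. States which of the three relationships place an event in the Device/Procedure-Related category, and uses the same rule for deaths in SAP 8.6.
5. Applies the SAP 4.8 missing-rating rule to the device relationship only, as it is written there.

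The cost is a few sentences in the SAP and a check against the case report form. No new data collection is needed if the form already records the three relationships. If it does not, item 3 must be limited to what is collected, and the SAP should say so.

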8.6 Deaths

The number of deaths will be tabulated with the primary cause of death respectively of device/procedure related or non-device related.

In addition, listing of deaths will be provided.

8.7 Vital Signs, Physical Findings and Other Observations Related to Safety

Data from vital signs (blood pressure, pulse rate and temperature) will be summarized by treatment arms. In addition, box plots of vital sign (Systolic Blood Pressure, Diastolic Blood Pressure, Mean Blood Pressure, Pulse Rate and Temperature) by visit (visit 1 to 5 and every 10th visit) will be presented for each treatment arm to show the evolution of the different vital sign parameters over time. The following ranges will be used to classified subjects within normal range and will be displayed on the box plots.

- Systolic Blood Pressure Result between [80; 180] mmHg
- Diastolic Blood Pressure between [40; 110] mmHg
- Mean Blood Pressure Result between [50; 150] mmHg
- Pulse Rate Result between [50; 150] Beats/min
- Temperature Result between [36; 38] °C / [96.8; 100.4] °F

The Acute pulmonary conditions will be displayed by treatment arm.

8.8 (Prior and) Concomitant Treatment

(Prior and) Concomitant medications including sedation (and the drugs used to treat adverse events or chronic diseases) will be classified according to World Health Organization Drug Dictionary (WHO-DD Version March 1, 2019).

The number and percentage of participants receiving a (prior or) concomitant medication will be displayed by anatomical main group (1st level of the Anatomical Therapeutic Chemical (ATC) classification) and chemical subgroup (4th level of the ATC classification) for the safety population.

Medications will be reported as prior when they start before the first day of ventilation.

Medications will be reported as concomitant when they start before, on or after first day of ventilation and continue afterwards.

Medications started before the first day of ventilation and continuing afterwards will be reported both as prior and concomitant.

(Prior and) Concomitant medication summaries will be sorted alphabetically by generic term within ATC class.

A listing of all medications recorded on the concomitant medications CRF page will provide details including indication, dose, route, frequency, and start and stop dates.

The type and cumulative dose of concomitant sedation and vasopressor used before and after randomization will be displayed by treatment arm.

Subjects ventilated during the practical training phase (Bedside training) will be monitored for safety events but will not be taken into consideration for the study outcome and statistics.

9. References

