7.2 Inclusion Criteria

Subjects must fulfill all of the following inclusion criteria to be eligible for enrollment into this study:

1. Age \geq 21 years old
2. Weight > 40 kilograms
3. Under invasive ventilation for less than 24 hours
4. Expected to be mechanically ventilated for at least 24 hours after enrollment
5. Agrees to not participate in other interventional research studies involving mechanical ventilation for the duration of study participation, unless approved by the DSMB
6. Signature of the informed consent by the subject or his/her next-of-kin according to country or state regulation

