8.1.2 Point of Enrollment and Randomization:

Subjects or next-of-kind or a legally authorized representative who sign and date the ICF and meet all of the study eligibility criteria will be eligible for inclusion into the EASiVENT Study.

Two different scenarios might occur:

1. The patient is already under invasive ventilation (intubated) for less than 24 hours, the next-of-kind or a legally authorized representative will sign and date the ICF.
2. The patient is able to sign and date the ICF before intubation.

The subject will only be considered enrolled when the **ICF signed and dated** and the subject will be **randomly assigned (1:1)** to automate ventilation with INTELLiVENT-ASV or to the non-automated ventilation.

Randomization will be stratified according to the clinical condition at inclusion (normal lungs, ARDS, chronic hypercapnia, brain injury). According to randomization allocation, the subject's attending physician will adjust the ventilator settings and recording will start.

Recording of ventilation data will start as randomization is completed and allocated randomization mode is selected.

Enrolled subjects will be documented on the Screening and Enrollment Log.

The investigator will maintain a log of all subjects screened and enrolled in the clinical study, assigning an identification code linked to their names, alternative subject identification or contact information. Patients who do not qualify for enrollment will be documented as ineligible on the Screening and Enrollment log.

Adverse Event collection will be started after point of enrollment.

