4.6 Calculated Variables

- Study day 0 is defined as the first day when study ventilation period starts.
- Baseline assessments done on the date of ventilation are assumed to take place before the study ventilation period starts, unless specified otherwise.
- Event durations in days (e.g., AE duration) are calculated as follows: [end date start date +1]. When applicable, Time durations in hours are calculated as follows: [end time start time]

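### SAP 8.8 leaves a drug used only on the first day of ventilation neither prior nor concomitant, and does not say which day that is

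*SAP*

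**What the plan says.** SAP 8.8, (Prior and) Concomitant Treatment, sets the classes in three sentences:

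- Prior: "Medications will be reported as prior when they start before the first day of ventilation".
- Concomitant: "Medications will be reported as concomitant when they start before, on or after first day of ventilation and continue afterwards".
- Both: "Medications started before the first day of ventilation and continuing afterwards will be reported both as prior and concomitant".

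The counts go into Table 14.03.11.01, by ATC level 1 and level 4, in the safety population. Randomisation appears in none of the three sentences, and the SAP does not define the first day of ventilation. The nearest definition is in SAP 4.6: "Study day 0 is defined as the first day when study ventilation period starts".

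The same section uses a different split for two drug groups: "The type and cumulative dose of concomitant sedation and vasopressor used before and after randomization will be displayed by treatment arm". It also promises a full listing: "A listing of all medications recorded on the concomitant medications CRF page will provide details including indication, dose, route, frequency, and start and stop dates".

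Under the protocol, ventilation can begin before allocation. Inclusion criterion 3 in Protocol 7.2 reads "Under invasive ventilation for less than 24 hours", and the first enrolment scenario in Protocol 8.1.2 is that "The patient is already under invasive ventilation (intubated) for less than 24 hours".

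**The concern.** A by-arm medication table should show what each arm received after allocation. This matters here because study staff know the allocation (Protocol 6.2.2) and care other than ventilation follows each site's own practice (Protocol 8.3.1).

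The rule has two weak places. First, the two classes do not cover every drug. The prior class needs a start before the anchor day, and the concomitant class needs use beyond it, so a drug confined to that day has no class. Second, the anchor is ambiguous. The day of intubation and the day of randomisation can differ, and the choice changes which drugs count as concomitant. As the text stands, the programmer has to choose.

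**Working it through.** The plan states no figure on this point, so there is none to reproduce. The check applies the sentences of SAP 8.8 to specific drug courses under three possible meanings of the anchor:

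- **Intubation day**: the calendar day ventilation began; continuing afterwards means use on a later day.
- **Study Day 0**: the calendar day of randomisation; continuing afterwards means use on a later day.
- **Clock time**: continuing afterwards means use after the hour ventilation began.

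*Subject 1: intubated 08:00, randomised 20:00 the same day.*

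| Drug course | Intubation day | Study Day 0 | Clock time |
|---|---|---|---|
| 08:30 to 09:00, before randomisation | neither | neither | concomitant |
| 21:00 to 22:00, after randomisation | neither | neither | concomitant |
| 08:30 to 19:00, stopped 1 h before randomisation | neither | neither | concomitant |
| Started the day before, stopped 19:00 | prior | prior | both |

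*Subject 2: intubated 18:00, randomised 12:00 the next day.*

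| Drug course | Intubation day | Study Day 0 | Clock time |
|---|---|---|---|
| 18:30 to 19:00 on the intubation day | neither | prior | concomitant |
| 13:00 to 14:00, after randomisation | concomitant | neither | concomitant |
| 18:30 to 11:00 next day, stopped 1 h before randomisation | concomitant | prior | concomitant |
| Started the day before intubation, stopped 1 h before randomisation | both | prior | both |

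**The gap.** On either day-level meaning, a drug confined to the anchor day is in neither class. That includes a drug given only after randomisation (second row for subject 1; under study Day 0, also second row for subject 2). The clock-time meaning closes the gap for these courses.

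**Pre-randomisation use counted as concomitant.** This never happens under study Day 0. Under the intubation-day meaning it needs randomisation on a later calendar day and use that passes the end of the intubation day but stops before randomisation. Under the clock-time meaning it is more general.

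**How often the two days differ.** The documents give no distribution. Assume, for subjects already ventilated at inclusion, a uniform hour of intubation and a uniform delay to randomisation between 0 and m hours. The chance that randomisation falls on a later calendar day is then (m/2)/24:

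- m = 6: 3/24 = 12.5%
- m = 12: 6/24 = 25%
- m = 24: 12/24 = 50%

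Simulation gave 12.5%, 25.0% and 49.8%. These are shares of subjects in whom the second problem could arise on the intubation-day meaning. They are not shares of misclassified drugs.

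**What dates alone can resolve.** SAP 8.8 mentions start and stop dates, not times. Take randomisation as falling within the 24-hour window. A drug started at intubation that runs past midnight and stops before randomisation must then stop on the randomisation date. No date-only rule can tell it from a drug still in use after randomisation.

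**The case against.** The strongest reply is that the anchor is already Day 0. SAP 4.1.1 labels randomisation as Day 0, SAP 4.6 ties Day 0 to the start of study ventilation, and its next item appears to use the date of ventilation for the same day. On that reading pre-randomisation use is not counted as concomitant, and the difference from the sedation and vasopressor split shrinks to day versus clock time. This is a fair reading, and it makes the second problem conditional. It does not settle the matter, because Protocol 8.2 records the start date and time of ventilation and SAP 3.2.2 counts ventilation duration from intubation. It also leaves the gap in place, on the day of randomisation itself.

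The second reply is that other outputs cover most of what matters. Sedation and vasopressors have their own displays around randomisation (Tables 14.03.11.02 to 14.03.11.04). Duration and dose of sedatives, analgesics, vasopressors and myorelaxants are secondary endpoints (Tables 14.02.02.05 and 14.02.02.06). Listing 16.02.09.02 shows every recorded drug. This stands: nothing is lost from the report. For other drugs, however, Table 14.03.11.01 is the by-arm medication summary. Sodium bicarbonate, named in the pH tables of both arms (Protocol 8.3.2 and 8.3.3), is an example.

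A reader might infer more: that both faults occur together, or that pre-randomisation use materially blurs the comparison of arms. The documents do not support either as a general statement. Of the three meanings, only the intubation-day one produces both faults, and then for different drug courses. No rates of drug use are given, so any figure for dilution would rest on invented inputs.

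**Conclusion.** The point holds as a minor fault of definition. On a plain day-level reading, whichever day is the anchor, drugs used only on that day are unclassified and missing from Table 14.03.11.01, including any given after randomisation. This assumes that the table is built from the two classes as defined. Separately, the anchor needs a definition, because on the intubation-day meaning some drugs stopped before randomisation can be reported as concomitant.

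The number of affected records cannot be derived from the documents. The consequence is limited to a descriptive safety table, and no endpoint, hypothesis test, sample size or error rate is touched.

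**What to change.** Replace the three classifying sentences in SAP 8.8 with:

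> Prior: started before randomisation. Concomitant: any use on or after randomisation, including single-day use. A drug meeting both is reported as both.

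State that randomisation (Day 0) is the split for every table in the section. Add that where only dates are held, use on the randomisation date counts as concomitant, and that this cannot separate use earlier on that date.

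The cost is a change of SAP wording and the matching program logic, with no new data, since start and stop dates are already to be listed. The change closes the single-day gap completely. It removes pre-randomisation use from the concomitant class completely only where drug times are held, and the documents do not show that they are.
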